4. STATISTICAL ANALYSES

4.1. General Considerations

4.1.1. General Methodology

The Full Analysis Set (FAS) will be used for all Study Population, Efficacy, Immunogenicity and PD analyses, unless otherwise stated. The Safety analysis set will be used for safety analyses, unless otherwise stated. PK analysis sets will be used for PK data analysis. FAS-Japan, Safety-Japan and PK-Japan will be used for Japan outputs. The Output and Programming Specification (OPS) document will provide more details.

Confidence intervals will use 95% confidence intervals (CI) unless otherwise specified.

Unless otherwise specified, continuous data will be summarised using descriptive statistics: n, mean, standard deviation (std), median, minimum and maximum. Categorical data will be summarised as the number and percentage of participants in each category.

For endpoints that are formally modelled, summary statistics will be provided. In the statistical analysis where covariates are included in the modelling, the following approach will be applied:

- The covariate of exacerbation history is classified as 2, 3, 4+. In the event that exacerbation history is <2, it will be included in the category of '2'.
- For the covariate of baseline pre-bronchodilator % predicted FEV1, screening prebronchodilator % predicted FEV1 will be used if baseline value is missing. If both sreeening and baseline pre-bronchodilator % predicted FEV1 are missing, a missing value will be assigned for this covariate.

Where statistical models are used, if there are important departures from the distributional assumptions, transformations of covariates or alternative models may be explored as supporting analyses.

Randomisation is stratified based on baseline ICS dose (medium or high). All statistical models will include this stratum as a covariate. In the case of wrong stratification assigned at the time of randomization, the analyses will be performed based on the data collected in the CRF, not the assigned stratum at randomization.

Assessments collected at withdrawal visit will be included in summary tables but won't be included in any statistical analysis.

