Efficacy Assessments																						
Review for exacerbations		X	X	X	X	X	X	X	X	X	X	X	X	X	X	X	X	X	X	X	Collection of exacerbations at Visit 1 is historical data.	
Spirometry (pre- and post-bronchodilator FEV ₁) ^h		X	X								X							X	X	FEV ₁ =Forced expiratory volume in 1 second; Spirometry should not be conducted for participants with confirmed/suspected COVID-19 (see Section 8.2.3).		
ACQ-5			X	X	X	X	X	X	X	X	X	X	X	X	X	X	X	X	X	X	ACQ-5=Asthma Control Questionnaire-5	
Review eDiary (asthma symptoms, PEF summary)			X	X	X	X	X	X	X	X	X	X	X	X	X	X	X	X	X	X	PEF=Peak expiratory flow	
HRQoL: PRO and Health Outcomes Assessments																						
SGRQ			X		X		X				X				X			X	X	SGRQ=St. George's Respiratory Questionnaire		
PROMIS (fatigue items)			X		X	X	X	X	X	X	X	X	X	X	X	X	X	X	X	X	PROMIS= Patient-reported outcomes measurement information system	
SNOT-22			X								X							X	X	SNOT-22=Sino-nasal Outcomes Test-22 Questionnaire		
Complete ADSD/ANSD			←===== daily =====→							X	X	X	X	X	X	X	X	X	X	ADSD/ANSD=Asthma Daily/Nightly Symptom Diary; To be completed daily during Run-in phase through Week 16, then to be completed for 1 full week during the week preceding each visit thereafter.		

Protocol Activity	Pre-Screening	Screening/Run-in	Intervention Period and Exit Visit (visit window is ±7 days)																	Follow-up/Withdrawal (±7 days)		Notes
			Visit	V0 ^a	Visit 1 ^a	V2 ^b R*	V3	V4	V5	V6	V7	V8	V9	V10	V11	V12	V13	V14	V15	V16	Exit V17	
Study Week	-8 to -6	-6 to -1	0	2	4	8	12	16	20	24	26	28	32	36	40	44	48	52	26 or 52	56	R* =Randomisation WS=Withdraw from study visit (see footnote c) FU=Follow-up visit/call (only required for participants not entering OLE study)	
Study Day	-56 to -42	-42 to -7	1	14	28	56	84	112	140	168	182	196	224	252	280	308	336	364		392		
Clinician-rated response to therapy							X				X				X				X	X		
Patient-rated response to therapy							X				X				X				X	X		
PGI-S		X	X				X		X		X				X				X	X	PGI-S: Patient Global Impression of Severity (of asthma)	
PGI-C							X		X		X				X				X	X	PGI-C: Patient Global Impression of Change (from baseline of asthma severity)	
Safety Assessments																						
Concomitant Medication Assessment	X	X	X	X	X	X	X	X	X	X	X	X	X	X	X	X	X	X	X	X	Ensure maintenance asthma medications from the year prior to Screening Visit 1, all medications within the 3 months prior to Screening Visit 1 and all current medications are reviewed.	

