The primary outcome measure will be the annualised rate of clinically significant exacerbations (i.e. exacerbations requiring systemic CSs and/or hospitalisation and/or ED visit [see [Section 8.2.2](#)]) measured over the 52-week treatment period. Additional efficacy assessments will include lung function (pre- and post-bronchodilator FEV₁), asthma control (ACQ-5), HRQoL measured with SGRQ, fatigue (PROMIS items), nasal symptoms (SNOT-22 questionnaire), daytime and night-time asthma symptoms (ADSD/ANSD), and daily electronic diary (eDiary) parameters including peak flow, rescue use, daily symptoms and nocturnal awakening due to asthma (see [Section 8.2](#)).

The study will include safety (see [Section 8.3](#) and [Section 8.4](#)) and immunogenicity (see [Section 8.8](#)) assessments to characterise the safety profile of GSK3511294 100 mg SC following repeat dosing. In addition, blood samples will be collected for assessment of PD effects (blood eosinophils) (see [Section 8.7](#)) and PK of GSK3511294 (see [Section 8.5](#)).

After randomisation, all participants will be encouraged to remain in the study and complete all scheduled visits, regardless of whether they receive the second dose of study intervention at Week 26. Participants who experience any of the study intervention

discontinuation conditions (listed in Section 7.1) will not receive another dose of study intervention.

Study visits may be conducted remotely (by a home healthcare professional) or virtually, however, in-person clinic visits are required for the following: pre-screening Visit 0, screening Visit 1, randomisation Visit 2, Visit 3, Visit 10, Visit 11, Exit Visit 17, and WS Visit (if applicable). Participants who are unable to attend their scheduled clinic visits due to COVID-19 restrictions or other unexpected events may complete some visits at home (see Appendix 11). Note: study intervention will only be administered in the clinic (at Week 0 and Week 26 visits).

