7.2. Participant Discontinuation/Withdrawal from the Study

- Participants are strongly encouraged to remain in the study for the entire duration but may prematurely withdraw from the study at any time at his/her own request, at the request of their legally authorised representative (LAR), or may be withdrawn at any time at the discretion of the investigator for safety, behavioural, or compliance reasons. This is expected to be uncommon.
- Participants who prematurely withdraw from the study should attend:
 - a Withdraw from Study (WS) Visit, 26 weeks after the last administered dose of study intervention (at Week 26 or Week 52) **AND**
 - a Follow-up visit/call, 30 weeks after the last administered dose of study intervention for AE/SAE and pregnancy assessments.

Note: this includes any participants who initially discontinue study intervention and remain in the study (Section 7.1) but later decide to withdraw from the study.

- If the participant withdraws consent for disclosure of future information, the Sponsor may retain and continue to use any data collected before such a withdrawal of consent.
- If a participant withdraws from the study, he/she may request destruction of any samples taken and not tested, and the investigator must document this in the site study records.

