Handling of missing data and intercurrent events leading to exclusion of data	
Missing data or data excluded due to intercurrent events will be handled as follows:
 
 For participants that discontinue study intervention due to reasons related to the COVID-19 pandemic, the observed data for the period following this intercurrent event will be excluded from the analysis. Data for this period will be assumed MAR (based on all data included in the analysis under the current estimand strategy). For participants that withdraw from the study, preventing assessment of the endpoint, the data for the period following withdrawal will be assumed MAR (using data collected under the proposed estimand strategy). 
Sensitivity analyses will be conducted to investigate the conclusions from deviations from these assumptions regarding missing and excluded data for (b) above. Missing data for participants will be based on data from participants who have discontinued study intervention (off-treatment) but remained in the study [Roger, 2019]. A tipping point analysis will also be conducted that will impute missing data based on a plausible range of means. The imputed means will be varied independently for treatment arms. Further details will be provided in the SAP.

The annualised rate of exacerbations requiring hospitalisation and/or ED visit over 52 weeks will be evaluated using the same strategy as that described for the primary endpoint (see Section 9.4.2).

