4.3.2. Main analytical approach for SGRQ total score, ACQ-5 score and pre-bronchodilator FEV₁

Secondary Endpoints Analyses
Endpoint(s)
 Change from baseline in SGRQ total score at Week 52 Change from baseline in ACQ-5 score at Week 52 Change from baseline in pre-bronchodilator FEV1 at Week 52
Model Specification
 Mixed Models Repeated Measures (MMRM) model. Terms in the model: Response: SGRQ Total score or ACQ-5 score or pre-bronchodilator FEV1 at each visit. Categorical: treatment group, exacerbation, baseline ICS dose (medium or high), exacerbation history (variable (2, 3, 4+)), geographical region, visit Continuous: baseline (SGRQ Total score, or ACQ-5 score, or baseline pre-bronchodilator FEV1), baseline pre-
 bronchodilator % predicted FEV1 (for SGRQ total score and ACQ-5 endpoints only) Interaction: baseline*visit, treatment group*visit Repeated: visit The MMRM analysis for SGRQ total scores will include data collected at Weeks 4, 12, 26, 40 and 52.
 The MMRM analysis for ACQ-5 score will include data collected at Weeks 2, 4, 8, 12, 16, 20, 24, 26, 28, 32, 36, 40, 44, 48 and 52. In the event the model fails to run due to too many assessment timepoints, timepoints included in the analysis may be reduced by keeping the timepoints of most interest. Suggested order for dropping timepoints is week 44, 20, 36, 16, 32, 8, 48, 24, 28.
 The MMRM analysis for pre-bronchodilator FEV1 will include data collected at Weeks 26 and 52. The model will be fit with an unstructured variance-covariance matrix.
 The Kenward and Roger method (KR) for approximating the denominator degrees of freedom and correcting for bias in the estimated variance-covariance of the fixed effects will be used. In the event the model fails to run using the KR method, then the residual method will be used instead. In the event the model fails to run using residual method and assessments are from many timepoints, timepoints included in the analysis may be reduced by keeping the timepoints/intervals of most interest. Baseline is defined in Section 4.1.2
 Two models will be fitted; one with a response variable of change from baseline and one with the response variable as the raw value.
Model Checking & Diagnostics

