4.3.4. Sensitivity analyses

The sensitivity analyses for the primary endpoint as described in Section 4.2.3 will also be performed for the secondary endpoints.

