4.4.5. PROMIS Fatigue items score

PROMIS Fatigue items score and change from baseline in PROMIS Fatigue items score will be summaried by treatment group and visit.

4.4.6. **SNOT-22** score

The SNOT-22 questionnaire is administered (post randomisation) at Week 26 and 52. The 22 questions of the SNOT-22 are each graded on a 6-point scale ranging from 0 = 'no symptoms' to 5 = 'as bad as things could be'. The scores for each of the questions are summed to derive the total score which ranges from 0 to 110, with higher scores representing worse quality of life.

Oth	her Endpoints Analyses
En	dpoint(s)
•	Change from baseline in SNOT-22 total score at Week 26 and Week 52
Мо	del Specification, Model Checking & Diagnostics
٠	See Model Specification, Model Checking & Diagnostics for secondary endpoints statistical analyses
•	analysis will include data collected at Weeks 26 and 52.
Мо	del Results Presentation
•	See Model Results Presentation for secondary endpoints statistical analyses (figures will not be presented)
•	SNOT-22 score (absolute value and changes from baseline) will also be summarised by treatment group and
	visit.

Other Endpoints Anal	yses

Handling of missing data and data excluded due to intercurrent events

- For participants that discontinue study intervention due to reasons related to the COVID-19 pandemic, the
 observed data for the period following this intercurrent event will be excluded from the analysis. Data for this
 period will be assumed MAR (based on all data included in the analysis under the current estimand strategy).
- For participants that withdraw from the study, preventing assessment of the endpoint, the data for the period following withdrawal will be assumed MAR (using data collected under the proposed estimand strategy).

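### SAP 4.1.1 keeps every withdrawal-visit value out of the models, so SGRQ, ACQ-5, FEV1 and SNOT-22 results observed in the Week 26 or Week 52 window are treated as missing

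*SAP*

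**What the plan says.** SAP 4.1.1 (General Methodology) sets the rule without exception: "Assessments collected at withdrawal visit will be included in summary tables but won't be included in any statistical analysis".

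Protocol 7.2 asks participants who leave the study early to attend "a Withdraw from Study (WS) Visit, 26 weeks after the last administered dose of study intervention (at Week 26 or Week 52". The schedule of activities (Protocol 1.3) heads these columns "Follow-up/Withdrawal (±7 days", the same width as the window for scheduled visits. Protocol 4.1 lists the visit among those that must take place in person: "Exit Visit 17, and WS Visit (if applicable".

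The schedule marks SGRQ, ACQ-5, spirometry and SNOT-22 at the WS visit, and Protocol 8.2.3.1 confirms spirometry at early withdrawal.

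Weeks 26 and 52 are modelled for all four measures. SAP 4.3.2 lists them for SGRQ (with Weeks 4, 12 and 40) and among the ACQ-5 visits. For FEV1 they are the only post-baseline visits: "The MMRM analysis for pre-bronchodilator FEV1 will include data collected at Weeks 26 and 52". SAP 4.4.6 says the same of SNOT-22: "analysis will include data collected at Weeks 26 and 52".

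On missing data, Protocol 9.4.3.1 says: "For participants that withdraw from the study, preventing assessment of the endpoint, the data for the period following withdrawal will be assumed MAR". SAP 4.3.2 repeats this. On sensitivity analyses, SAP 4.3.4 says: "The sensitivity analyses for the primary endpoint as described in Section 4.2.3 will also be performed for the secondary endpoints".

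**The concern.** Keeping withdrawal-visit data out of a repeated-measures model makes sense when such visits happen at any time and match no modelled visit. Here the protocol deliberately places the WS visit at a modelled visit. The SAP has no rule assigning an in-window WS value to Week 26 or Week 52, so that value appears in a summary table while the model treats the visit as missing at random (MAR).

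SGRQ, ACQ-5 and FEV1 at Week 52 are steps 2 to 4 of the alpha-controlled hierarchy (SAP 2.1). For these, an observed outcome is replaced by an assumption that the outcome itself could help to check. For FEV1 and SNOT-22, someone who leaves after dose 1 but before Visit 10, and attends the WS visit at Week 26, loses their only post-baseline value in the model.

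The rule also sits uneasily with wording that ties MAR to withdrawal that prevents assessment of the endpoint. An in-window measurement shows that the endpoint was assessed. This is a tension rather than a clear contradiction. Protocol 9.4.3.1 contains no WS exclusion, and SAP 4.12 does not list one among the changes to protocol-defined analyses.

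**Working it through.** **Is the measure collected at the WS visit?** The column layout is partly lost in the extracted schedule, so the marks were counted. SGRQ has seven: baseline and the five modelled weeks explain six, leaving one for WS. SNOT-22 has four: baseline, Weeks 26 and 52, and WS. The ACQ-5 row continues past Visit 17. Spirometry is confirmed in Protocol 8.2.3.1. The ADSD/ANSD row has ten marks after its daily period, which match Visits 8 to 17 and leave none for WS.

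**The plan's own power figures.** Inputs from Protocol 9.2.1.2 and SAP 5.1.2: 250 vs 125, two-sided 5%; SGRQ difference 7, SD 17; ACQ-5 difference 0.35, SD 1.1. With SE = SD × √(1/250 + 1/125) and power = Φ(difference/SE − 1.96):

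| Missing at Week 52 | SGRQ power | ACQ-5 power |
|---|---|---|
| 0% | 96.4% (stated 96%) | 82.8% (stated 83%) |
| 10.5% | 94.5% | 78.5% |
| 14% | 93.65% | 76.8% |

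The stated figures are reproduced only with all 375 observed, so they carry no allowance for missing values.

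**How many values are discarded?** The documents give no WS attendance, so these are assumptions:
- 14% withdraw. This is borrowed from the primary endpoint's participant-years figure in SAP 5.1.1 and is not a headcount.
- Half leave before dose 2 and half after.
- In-window WS attendance is 25% to 100%, with 50% as the illustration.

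Share of an arm with a discarded Week 52 value: w = 0.14 × 0.5 × attendance = 1.75%, 3.5% or 7%. In the illustration, 0.035 × 375 ≈ 13 participants.

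**Possible shift.** If the discarded values differ from their MAR prediction by d on average, the arm mean shifts by w × d. The treatment difference shifts by that amount only if one arm alone is affected; equal shifts cancel. At 86% observed, the SE of the difference is 2.008 for SGRQ and 0.130 for ACQ-5.

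| | SGRQ | ACQ-5 |
|---|---|---|
| Low | 0.0175 × 2 = 0.035 | 0.0175 × 0.1 = 0.002 |
| Illustration, d = full assumed effect | 0.035 × 7 = 0.245 (0.12 SE) | 0.035 × 0.35 = 0.012 (0.09 SE) |
| Extreme, full attendance | 0.07 × 7 = 0.49 (0.24 SE) | 0.07 × 0.35 = 0.025 (0.19 SE) |

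**Precision, ACQ-5.** In the illustration, missingness falls from 14% to 14% − 3.5% = 10.5%. On complete cases, power rises from 76.8% to 78.5% (1.6 points before rounding). An MMRM borrows from earlier visits. With one earlier value correlated r with Week 52 and monotone dropout, the variance factor is (1 − r²)/(1 − missing) + r². Then:
- r = 0.5: 78.29% to 79.52%, a gain of 1.2 points
- r = 0.8: 80.60% to 81.20%, a gain of 0.6 points

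Over 25% to 100% attendance the gain runs from 0.3 to 2.4 points.

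**Precision, FEV1.** Adding m participants with a Week 26 value only to n = 0.86 × 375 = 322.5 with both values cuts the variance of the Week 52 mean by r² × m/(n + m). With m = 13.1 this is 0.98% (r = 0.5) to 2.5% (r = 0.8). Over the full range it is 0.5% (m = 6.56, r = 0.5) to 4.8% (m = 26.25, r = 0.8).

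**The case against.** The rule is explicit, pre-specified, applied to both arms, and keeps the values visible in summary tables. Participants who stop dosing but stay in the study already contribute their Week 26 and Week 52 values. Only those who leave the study and still return in person are affected, and attendance is something they should do rather than must. Some WS visits will miss the window. Dose 2 has its own ±7-day allowance, Protocol Appendix 11 permits a 28-week dose interval (which puts WS near Week 54), and someone who skips dose 2 and withdraws late has already passed the 26-week point. MAR is also stress-tested by off-treatment imputation and a tipping-point analysis, and the computed shifts are about a tenth of a standard error.

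Much of this stands. The affected group is small, off-window visits are outside this point, and the effect is modest. The illustration's d is generous too: participants with a Week 52 WS value have had both doses and are about 26 weeks from the last, the coverage that SAP 4.6.1 assigns to a dose, so loss of benefit cannot be presumed.

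It does not remove the point. A summary table does not put the observed value into the test. As written, the sensitivity analyses impute the period after withdrawal and do not use WS values. Both are conditional: SAP 4.2.3.1 on data thresholds, SAP 4.2.3.2 on a significant result. SAP 4.3.4 extends them to the secondary endpoints without visit-level detail. Footnote c of the schedule and the Output and Programming Specification, to which SAP 1 defers data-handling detail, could not be checked. A programming specification could not properly override an explicit SAP rule.

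**Conclusion.** The concern holds. As written, observed in-window Week 26 and Week 52 values of SGRQ, ACQ-5, FEV1 and SNOT-22 are excluded from the models and handled as MAR.

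The size depends on WS attendance, which the documents do not give. Under the stated assumptions, the possible shift runs from negligible to about a quarter of a standard error in a one-sided extreme, and its direction is not guaranteed. The precision gain from using the values is small. No breach of the treatment-policy strategy is claimed. Confidence is medium because of the two unseen sources. The change is worth making because the data are already collected, three of the endpoints are alpha-controlled, and the correction is very cheap.

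**What to change.** Replace the sentence in SAP 4.1.1 with text along these lines:

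> For SGRQ, ACQ-5, pre- and post-bronchodilator FEV1 and SNOT-22 (including the SGRQ and ACQ-5 responder analyses), WS assessments within ±7 days of Week 26 or Week 52 are assigned to that visit if no scheduled-visit value exists, and are included in the models. Data after COVID-19-related discontinuation remain excluded. All other WS assessments, including blood eosinophils, are summarised only.

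In SAP 4.3.4, add that for these visit-based endpoints imputation applies only to visits still missing after this mapping.

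Naming the endpoints matters. Blood eosinophils are also analysed by MMRM (SAP 4.5.2), and their estimand in SAP 1.1.2 excludes counts taken more than 26 weeks after the last dose. The primary exacerbation model stays as it is.

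Cost: one SAP sentence replaced by the mapping text, one clause, and a visit-mapping rule in the programming specification. No new data collection.

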4.1.2. Baseline Definition

Baseline values for visit based assessments and eDiary assessments are defined in Table 3.

Unless otherwise stated, if baseline is missing, no derivation will be performed and baseline will be set to missing.

Parameter	Study Assessments Collected Prior to Dosing		Baseline Definition	
	Screening (Visit 1)	Day 1 Pre-Dose (Visit 2)		
Efficacy, Health Outcom	nes and Other			
SGRQ total and domain		Х	Day 1 pre-dose	
scores				
ACQ-5		Х	Day 1 pre-dose	
Pre-bronchodilator FEV ₁	Х	X	Day 1 pre-dose	
Post-bronchodilator FEV ₁	Х	X	Day 1 pre-dose	
PROMIS Fatigue items score		X	Day 1 pre-dose	
ADSD/ANSD weekly mean score	X (daily following Screening)		Average of measurements from Day -7 to Day -1 inclusive (at least 4 days must be non-missing)	
Awakenings at night due to asthma symptoms requiring rescue medication use 2-week mean	X (daily followin	g Screening)	Average of measurements from Day -7 to Day -1 inclusive (at least 4 days must be non-missing)	
Morning PEF 2-week mean	X (daily followin	g Screening)	Average of measurements from Day -6 to Day 1(pre-dose) inclusive (at least 4 days must be non-missing)	
Daily asthma symptom scores 2-week mean	X (daily followin	g Screening)	Average of measurements from Day -6 to Day 1(pre-dose) inclusive (at least 4 days must be non-missing)	
Mean number of occasions of rescue medication use/day 2-week mean	X (daily followin	g Screening)	Average of measurements from Day -6 to Day 1(pre-dose) inclusive (at least 4 days must be non-missing)	
SNOT-22 score		Х	Day 1 pre-dose	
PGI-S	Х	Х	Day 1 pre-dose	
Safety				
Blood pressure	X	X	Values from most recent assessment prior to first dose of study treatment which records both systolic and diastolic BP	
Pulse rate	Х	X	Most recent individual value prior to first dose of study treatment	
Clinical Chemistry	Х	Х	Most recent individual value prior to first dose of study treatment	
ECG endpoints	Х	X	Values from most recent ECG conducted prior to first dose of study treatment	
Hematology with differential (including eosinophil count)	X	X	Most recent individual value prior to first dose of study treatment	
Other				
Complement C3 and C4		X	Day 1 pre-dose	
Immunogenicity		Х	Day 1 pre-dose	

Table 3Baseline Definitions & Derivations

NOTES :

- Only records that have been assigned a treatment phase of 'pre-treatment' will be considered as baseline assessments.
- ADSD is to be completed before going to bed and refers to asthma symptoms during the day. Day 1
 assessment of ADSD will not be pre-dose. Therefore an average of measurements from Day -7 to Day -1 is
 defined as the baseline for ADSD/ANSD.
- Baseline Definitions will be used for derivations for endpoints / parameters and indicated on summaries and listings.
- Unless otherwise stated, if baseline data is missing no derivation will be performed and will be set to missing.

